#### **3.2 Study Endpoints**

##### **3.2.1 Primary Endpoints and Definitions**

###### **(1) Local Recurrence (LR)**

Local recurrence is defined as a pathologically confirmed reappearance of PT in the ipsilateral breast, chest wall, or axillary lymph nodes after initial surgery. Diagnosis is confirmed by postoperative follow-up records (outpatient visits, hospital admissions, imaging findings) and pathology reports.

###### **(2) Local Recurrence Rate (%)**

The percentage of patients with local recurrence among the total study population.

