**(3) Recurrence-Free Survival (RFS)**

The time interval (in months) from the date of initial surgery to the date of first pathologically confirmed local recurrence. Patients without recurrence are censored at the date of last follow-up.

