**(4) Cumulative Recurrence Rate**

The cumulative probability of local recurrence at 1, 3, 5, and 10 years after surgery, estimated by the Kaplan-Meier method or competing risk method.

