**(6) Distant Metastasis Rate (%)**

The percentage of patients with distant metastasis among the total study population.

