**(8) Cumulative Metastasis Rate**

The cumulative probability of distant metastasis at 1, 3, 5, and 10 years after surgery.

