##### **(2) Analysis of primary endpoints**

- **Local recurrence (LR):** Recurrence-free survival (RFS) curves will be plotted using the Kaplan-Meier method, and cumulative recurrence-free rates at 1, 3, 5,

and 10 years will be calculated. Univariate analysis using log-rank test; multivariable analysis using Cox proportional hazards regression (hazard ratios and 95% CI). When death is a competing risk for recurrence, cumulative incidence functions (CIF) and Fine-Gray competing risk models will be used.

- **Distant metastasis (DM):** Similarly, distant metastasis-free survival (DMFS) will be analyzed using Kaplan-Meier and Cox regression, with death as competing event.
- **Overall survival (OS):** Kaplan-Meier method will estimate median OS and 1-, 3-, 5-, 10-year survival rates. Cox regression will identify influencing factors.

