### **(3) Analysis of secondary endpoints**

Secondary endpoints (demographic, tumor, treatment characteristics) will mainly be analyzed using descriptive statistics and between-group comparisons as described in (1). Additional exploratory analyses will include these variables as covariates in Cox or logistic regression to assess associations with primary outcomes. Latent class analysis may be used to identify subtypes based on tumor characteristics.

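### LR and DM rates are primary endpoints defined as crude percentages with no time horizon, and the plan does not fix the competing-risk estimator that would replace them

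*Combined protocol and SAP*

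**What the plan says.** Under the heading "Primary Endpoints and Definitions", section 3.2.1 lists several measures for each event.

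- **Crude rates.** Item (2), the LR rate, is "The percentage of patients with local recurrence among the total study population". Item (6), the DM rate, is "The percentage of patients with distant metastasis among the total study population". Neither carries a time point.
- **Time-based rates.** Item (4) gives cumulative LR at 1, 3, 5 and 10 years, "estimated by the Kaplan-Meier method or competing risk method". Item (8) is "The cumulative probability of distant metastasis at 1, 3, 5, and 10 years after surgery", with no estimator named.
- **Censoring.** For RFS, item (3) states: "Patients without recurrence are censored at the date of last follow-up". Item (7) has the matching rule for DMFS. A patient who dies without the event is therefore censored.

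Section 5.4.2 (2) plans Kaplan-Meier and Cox for LR. It adds cumulative incidence functions and Fine-Gray models on the condition that death is a competing risk. For DM it says that "distant metastasis-free survival (DMFS) will be analyzed using Kaplan-Meier and Cox regression, with death as competing event". Section 5.4.2 (1) places the crude LR, DM and tumour-specific mortality rates under descriptive analysis, overall and by grade. Section 5.4.2 (3) allows exploratory models with patient and tumour characteristics as "covariates in Cox or logistic regression to assess associations with primary outcomes".

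Section 5.1 sets the surgery window at January 2001 to December 2023. No end-of-follow-up date or minimum follow-up is given. Patients with under 6 months of follow-up are removed only in a sensitivity analysis (section 5.4.2 (6)).

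**The concern.** A crude percentage gives a patient operated on in 2001 and one operated on in late 2023 the same weight in the denominator, although they can have been observed for very different times. The result is a risk at no particular time. It cannot be set beside a 5- or 10-year figure from this cohort or any other, and two grades can be compared fairly only if their follow-up is alike.

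The time-based measures should solve this, but the plan does not say which estimator is primary. Death always precludes a later first recurrence or metastasis, so a condition that death be a competing risk is always met and gives no rule for choosing. For DM the wording asks Kaplan-Meier to handle a competing event. With deaths censored it cannot: one minus Kaplan-Meier then estimates risk as if nobody died of anything else, and exceeds the proportion of patients who actually metastasise.

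At stake are the study's main frequencies. With crude, Kaplan-Meier and competing-risk versions all permitted, the figure to emphasise could be chosen after the results are seen. Logistic regression on the same outcomes would also ignore follow-up time.

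**Working it through.** **The plan's own figure.** Section 5.4.1 expects about 380 LR events from about 3,500 patients at roughly 11%.

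- 3,500 × 0.11 = 385.
- With the 7:2:1 grade mix (section 5.4.1) and recurrence rates of 7.1%, 16.7% and 25.1% (section 2.2.2): 0.7 × 7.1 + 0.2 × 16.7 + 0.1 × 25.1 = 10.82%, and 3,500 × 0.1082 = 379.

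The figure reproduces. It is itself a crude proportion with no time horizon.

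**Step 1: how far the crude rate depends on follow-up.** The documents give no follow-up distribution, death rate or cut-off, so the following are assumptions: 10-year cumulative incidence of LR 11%; deaths 0.2% per year (d = 0.002); surgery dates uniform over 23 years; cut-off at the end of 2025, so potential follow-up is 2 to 25 years; observation ending early at a yearly rate c.

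With constant hazards, CIF(t) = h/(h+d) × [1 − exp(−(h+d)t)]. Setting CIF(10) = 0.11 gives h = 0.01178. With k = h + d + c, the expected crude proportion is

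(h/k) × {1 − [exp(−2k) − exp(−25k)]/(23k)}.

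| Loss per year (c) | Crude LR | Events in 3,500 |
|---|---|---|
| 0 | 14.2% | 497 |
| 5% | 9.9% | 348 |
| 10% | 7.4% | 260 |
| 20% | 4.8% | 167 |

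The true risk is the same in every row: 5.7% at 5 years and 11.0% at 10 years. Moving the cut-off to the end of 2024 changes the no-loss value from 14.2% to 13.2%.

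If recurrence is front-loaded (exponential with mean 2.5 years among those who ever recur, deaths ignored, 10-year risk still 11%), the crude value runs from 10.7% with no loss to 7.3% at 20% loss (373 to 256 events). The dependence is weaker but remains.

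**Step 2: Kaplan-Meier against cumulative incidence at 10 years.** Let a = −ln(1 − KM risk)/10 and b = −ln(1 − D)/10, where D is the assumed 10-year risk of death without the event. Then CIF = a/(a+b) × [1 − exp(−10(a+b))].

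Malignant tumours, taking the 25.1% of section 2.2.2 as a 10-year 1−KM value (assumed; the source figure has no horizon), a = 0.02890:

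- D = 20%: b = 0.02231, CIF = 22.6%, overstatement 25.1/22.6 − 1 = 11%.
- D = 30%: b = 0.03567, CIF = 21.3%, overstatement 18%.
- D = 40%: b = 0.05108, CIF = 19.9%, overstatement 26%.

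Low mortality, 1−KM of 11%, a = 0.01165:

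- D = 2%: CIF = 10.9%, overstatement 1.0%.
- D = 5%: CIF = 10.7%, overstatement 2.5%.

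The overstatement grows with mortality, so it need not be equal across the grade strata of section 5.4.2 (6).

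**The case against.** The strongest reply is that the plan already holds the right tools. Section 3.2.1 (4) permits a competing-risk method. Section 5.4.2 (2) names cumulative incidence and Fine-Gray for LR and recognises death as a competing event for DM. Section 5.1 lists competing risk models, and section 5.4.2 names tidycmprsk and mstate. Section 5.4.2 (6) adds a competing-risk analysis of death from phyllodes tumour against other causes. The crude rates sit under descriptive analysis, while the primary-endpoint analysis is wholly time-to-event. Logistic regression is only an exploratory alternative to Cox. All of this stands. A reader might infer that the plan offers no valid estimator of actual risk; the documents do not support that. What remains is that the valid estimator is optional for LR and unnamed for DM.

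A reader might also expect a spurious fall in crude recurrence across calendar periods. Shorter follow-up of recent operations could produce one, but no such table is planned. The 5-year intervals in section 5.4.2 (1) apply to treatment patterns, and outcome rates are planned overall and by grade. For the planned comparison, distortion requires follow-up to differ by grade, which the documents neither show nor rule out.

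A third tempting reading is that Kaplan-Meier would be badly wrong for the whole cohort. About 70% of patients are expected to be benign, and section 2.2.4 says benign tumours do not significantly affect overall survival. Where mortality is low the gap is very small.

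Finally, section 4.2 (3) excludes patients lost to follow-up, so the higher loss rates in the illustration may not apply. Even with no loss, however, the crude 14.2% matches neither the 5-year nor the 10-year risk.

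**Conclusion.** The concern holds as a defect of specification that should be fixed; it is not a missing method. Two primary endpoints are percentages with no time horizon, in a cohort whose follow-up must be uneven. Their dependence on follow-up is strong under a constant hazard (about 14% down to 5% for one 11% 10-year risk) and moderate if recurrence comes early (10.7% to 7.3%). The time-based estimator is left open for LR and is internally inconsistent for DM.

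The Kaplan-Meier overstatement is about 1 to 2.5% relative at 10-year mortality of 2 to 5%. In malignant tumours it could be 11 to 26%, if 10-year death without LR is 20 to 40%.

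The cut-off, loss rates, death rates and 10-year horizons are all assumptions. The direction of each effect does not depend on them, but the size does. No single corrected figure can be derived from the documents.

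**What to change.** 1. In sections 3.2.1 and 5.4.2 (2), name the cumulative incidence function (Aalen-Johansen, death as competing event) at 1, 3, 5 and 10 years as the single primary estimator for LR and for DM, overall and by grade. Remove the choice of method in the LR definition and the conditional wording in section 5.4.2 (2), and replace the DM sentence.
2. Use the same estimator for the tumour-specific mortality rate in section 5.4.2 (1), with death from other causes as the competing event.
3. State the follow-up cut-off date.
4. Relabel the crude LR and DM percentages as descriptive counts, reported beside median follow-up by reverse Kaplan-Meier, and take them off the primary list.
5. In section 5.4.2 (3), use time-to-event models rather than logistic regression for associations with these outcomes.
6. Tie the expected 380 events in section 5.4.1 to a stated follow-up assumption.

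The cost is SAP wording, and the crude percentage loses its headline status. A package for cumulative incidence, tidycmprsk, is already listed. The cut-off date is the only new item of information needed for items 1 to 5.

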**(3) Recurrence-Free Survival (RFS)**

The time interval (in months) from the date of initial surgery to the date of first pathologically confirmed local recurrence. Patients without recurrence are censored at the date of last follow-up.

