**(7) Distant Metastasis-Free Survival (DMFS)**

The time interval (in months) from the date of initial surgery to the date of first distant metastasis. Patients without metastasis are censored at the date of last follow-up.

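### The endpoints named recurrence-free survival and distant metastasis-free survival do not count death (nor, for RFS, metastasis), so label, event set and estimator do not match

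*Combined protocol and SAP*

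**What the plan says.** All references are to the combined protocol and SAP.

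- **RFS, section 3.2.1 (3).** The interval runs "from the date of initial surgery to the date of first pathologically confirmed local recurrence. Patients without recurrence are censored" at last follow-up. Section 3.2.1 (1) limits local recurrence (LR) to "pathologically confirmed reappearance of PT in the ipsilateral breast, chest wall, or axillary lymph nodes after initial surgery", so distant disease is not an RFS event.
- **DMFS, section 3.2.1 (7).** The interval runs "from the date of initial surgery to the date of first distant metastasis", and "Patients without metastasis are censored at the date of last follow-up".
- **OS, section 3.2.1 (9).** The event is death from any cause.
- **Analysis, section 5.4.2 (2).** RFS curves are Kaplan-Meier. Cumulative incidence functions and Fine-Gray models are added for LR where death competes. For metastasis, "distant metastasis-free survival (DMFS) will be analyzed using Kaplan-Meier and Cox regression, with death as competing event".
- **Timed rates.** Section 3.2.1 (4) leaves the choice between Kaplan-Meier and a competing-risk method open for recurrence. Section 3.2.1 (8) names no method for metastasis.
- **Sensitivity analyses, section 5.4.2 (6).** None adds death or metastasis to RFS, or death to DMFS.

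**The concern.** A quantity called recurrence-free or metastasis-free survival is normally read as the probability of being alive without the event. As written, a patient with lung metastases at month 12 who dies at month 20 with no pathologically confirmed local event never has an RFS event. Until death that patient stays in the RFS risk set as recurrence-free.

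For DMFS, the name implies that death is an event, the definition treats it as censoring, and the analysis section calls it competing while naming Kaplan-Meier and Cox. Those are three different treatments of death for one primary endpoint.

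What is at stake is the meaning of the headline curves. No listed primary endpoint gives the chance of being alive and disease-free, yet two carry names that suggest they do. DMFS can also lie above OS, which cannot happen when death is a DMFS event. This is most plausible in benign tumours. They are about 70% of the expected cohort (7:2:1, section 5.4.1), and section 2.2.4 says that benign disease has no significant effect on OS, so deaths there should be mostly unrelated to the tumour.

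**Working it through.** **1. The plan's own figure.** Section 5.4.1 expects about 380 LR events.
- 3,500 × 0.11 = 385.
- Weighting the grade-specific rates of section 2.2.2 by 7:2:1: 0.7 × 7.1% + 0.2 × 16.7% + 0.1 × 25.1% = 10.82%, and 3,500 × 0.1082 = 378.7.

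The figure reproduces, and it counts local recurrence only. The sample size argument therefore rests on time to local recurrence, not on a composite.

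**2. A count without a model.** Take 100 patients followed completely. Five develop metastasis and die, and ten die without metastasis. OS is 85%. DMFS as defined is 1 − 5/100 = 95% if the metastases come before the other deaths, and 1 − 5/90 = 94.4% if they come after. A DMFS that counts death is 85%.

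**3. Inputs for an illustration at 10 years.**
- From the documents: LR 25.1% and metastasis (DM) 6.5% to 62.5% in malignant tumours (section 2.1), and overall LR 11% (section 5.4.1). Sections 2.1 and 5.4.1 give no time horizon; I treat the rates as 10-year risks.
- Assumed: whole-cohort DM 2%; malignant DM 20% as a middle value; death without DM 1% to 10%; median survival after DM 1.5 years; constant, independent hazards.

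**4. Formulas.** Let m and d be the hazards of DM and of death without DM, each −ln(1 − risk)/10. Let a = m + d, let k = ln 2/1.5 be the death hazard after DM, and let T = 10.
- DMFS as defined = exp(−mT) = 1 − DM risk.
- DMFS counting death = exp(−aT) = (1 − DM risk)(1 − death risk).
- OS = exp(−aT) + m[exp(−aT) − exp(−kT)]/(k − a).
- RFS as defined = 1 − LR risk.
- Composite RFS = (1 − LR risk)(1 − DM risk)(1 − death risk).

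**5. DMFS results (%).**

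| Setting | DM risk | Death without DM | DMFS as defined | OS | DMFS counting death |
|---|---|---|---|---|---|
| Whole cohort | 2 | 1 | 98.0 | 97.4 | 97.0 |
| Whole cohort | 2 | 3 | 98.0 | 95.5 | 95.1 |
| Whole cohort | 2 | 5 | 98.0 | 93.5 | 93.1 |
| Benign | about 0 | 3 | 100.0 | 97.0 | 97.0 |
| Malignant | 6.5 | 5 | 93.5 | 90.1 | 88.8 |
| Malignant | 20 | 10 | 80.0 | 75.7 | 72.0 |
| Malignant | 62.5 | 5 | 37.5 | 45.1 | 35.6 |

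In the whole cohort, DMFS as defined is 1.0 to 4.9 points above a DMFS counting death, and 0.6 to 4.5 points above OS. In the last row it is below OS, so the ordering is not fixed.

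**6. RFS results.**
- Malignant, DM 6.5%: 74.9% as defined. Composite 0.749 × 0.935 × (0.99, 0.95, 0.90) = 69.3%, 66.5%, 63.0% for 1%, 5%, 10% death without DM. The gap is 5.6, 8.4 or 11.9 points.
- Malignant, DM 20%, 5% death: 0.749 × 0.80 × 0.95 = 56.9%, a gap of 18.0 points.
- Whole cohort, LR 11%, DM 2%, death 1% to 5%: 89.0% as defined against 86.3% to 82.9%, a gap of 2.7 to 6.1 points.

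**7. Does the planned cumulative incidence function remove this?** No. One minus the cumulative incidence of DM counts patients who died without DM as event-free. At DM 20% and death 10% it is 81.0%, against 80.0% by Kaplan-Meier. It is the right tool for the incidence of metastasis, but it does not produce a survival endpoint.

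**The case against.** The strongest reply is that this is a matter of labels. Section 1 names the primary outcomes as LR, DM and OS. The RFS curve is introduced under LR, the sample size is built on LR, and the definitions state their events openly. Read as time to metastasis, DMFS with death competing is coherent. Section 5.4.2 (2) acknowledges competing death, and OS is reported at the same time points. That much stands: the event sets match the stated LR and DM outcomes, and renaming would cure the label.

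A reader might go further in four ways that the documents do not support.
- *The event sets are themselves wrong.* They suit the LR and DM outcomes; the names and the choice of estimator do not suit them.
- *The dead are carried forward as recurrence-free.* In the Kaplan-Meier analysis they are censored. They count as event-free only in one minus the cumulative incidence and in the crude percentages of sections 3.2.1 (2) and (6).
- *The primary endpoints contradict each other, or DMFS must exceed OS.* Time to metastasis and time to death are different quantities, and with frequent metastasis the order can reverse.
- *RFS is biased by as much as 48 points in malignant disease.* That figure (74.9% against 26.7%) uses the 62.5% extreme of a wide literature range, in about 10% of the cohort. It compares two estimands. Positive dependence between LR, DM and death would narrow it.

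What the reply does not answer is that Kaplan-Meier curves labelled RFS and DMFS are planned, that metastasis has no role in RFS, and that DMFS is assigned Kaplan-Meier and Cox together with a competing event.

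**Conclusion.** The point holds as a mismatch between label, event set and estimator in two primary endpoints. It is more than clerical, because it changes what the reported figures mean, and it should be corrected before analysis.

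Its size depends on death rates that the documents do not supply. Under the assumptions above, the whole-cohort DMFS gap is about 1 to 5 points. The malignant RFS gap is about 8 points at 6.5% metastasis and 5% death without metastasis, and it grows with the metastasis rate. Both rest on independent constant hazards and on reading the quoted rates as 10-year risks. That DMFS can exceed OS follows from the definitions alone; how often it would do so cannot be determined from the documents.

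**What to change.** 1. In sections 3.2.1 (3) and (7), rename the quantities time to local recurrence and time to distant metastasis. Keep them as the LR and DM primary endpoints, so that the figure of about 380 events in section 5.4.1 stands.
2. In sections 3.2.1 (4), 3.2.1 (8) and 5.4.2 (2), estimate both by cumulative incidence with death as the competing event, without the conditional wording for LR or the open choice of method.
3. If the names RFS and DMFS are kept, define RFS as time to the first of LR, DM or death from any cause, and DMFS as time to the first of DM or death. Estimate these by Kaplan-Meier and Cox. In section 5.4.2 (2), move the competing-event clause from DMFS to time to distant metastasis.

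The cost is some wording and, under step 3, two derived variables. Section 5.3 (2) already has recurrence, metastasis and death extracted in duplicate, so no new data collection should be needed. The downside is that composite RFS and DMFS will look less favourable. If a composite RFS replaced LR as the primary endpoint, the event count and the events-per-variable argument would have to be restated; steps 1 and 2 avoid that.

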**(4) Cumulative Recurrence Rate**

The cumulative probability of local recurrence at 1, 3, 5, and 10 years after surgery, estimated by the Kaplan-Meier method or competing risk method.

**(5) Distant Metastasis (DM)**

Distant metastasis is defined as radiologically (CT, PET-CT, bone scan, etc.) and/or pathologically confirmed spread to organs outside the breast (lung, liver, bone, brain, etc.).

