## **4. Study Population**

### **4.1 Inclusion Criteria**

(1) Patients with a postoperative paraffin-embedded pathology diagnosis of breast phyllodes tumor (benign, borderline, or malignant) according to WHO criteria.

(2) Patients who underwent surgical treatment at any participating center during the designated time period.

(3) Patients with complete or reasonably complete clinical records, pathology reports, and follow-up data sufficient to extract the core variables required by the study protocol.

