### **6.2.3 Data Integrity Checks**

- **Source Data Verification (SDV):** The project team will randomly select 10% of cases. A quality control officer will compare the data in the eCRF with the original hospital electronic medical records item by item to ensure transcription accuracy.
- **Logical Checks:** Logic validation rules will be embedded at the database design stage (e.g., surgery date cannot be later than recurrence date; tumor size cannot be negative). The system will automatically flag data points that violate logic, requiring mandatory review.
- **Missing Value Management:** The system will generate regular missing value reports. For critical variables (e.g., pathological grade, surgical margin status, follow-up outcomes), every effort will be made to trace back to medical records for supplementation. If supplementation is truly impossible, the value will be clearly recorded as "missing" and its impact will be assessed in subsequent statistical analyses.

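### Distant metastasis (DM) is not limited to events after surgery, so metastases already present at initial surgery count in the primary DM rate and have no stated handling in DMFS

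*Combined protocol and SAP*

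**What the plan says.** All places are in the combined protocol and SAP.

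- **DM definition, 3.2.1 (5):** "Distant metastasis is defined as radiologically (CT, PET-CT, bone scan, etc.) and/or pathologically confirmed spread to organs outside the breast". No time condition is attached.
- **DM rate, 3.2.1 (6):** "The percentage of patients with distant metastasis among the total study population". It has no time origin and no at-risk restriction.
- **DMFS, 3.2.1 (7):** "The time interval (in months) from the date of initial surgery to the date of first distant metastasis".
- **Cumulative metastasis rate, 3.2.1 (8):** "The cumulative probability of distant metastasis at 1, 3, 5, and 10 years after surgery".
- **Local recurrence, 3.2.1 (1), for contrast:** "reappearance of PT in the ipsilateral breast, chest wall, or axillary lymph nodes after initial surgery". Here the time condition is explicit.
- **Entry, 4.1:** "Patients with a postoperative paraffin-embedded pathology diagnosis of breast phyllodes tumor (benign, borderline, or malignant) according to WHO criteria" and "Patients who underwent surgical treatment at any participating center during the designated time period", plus a requirement for adequate records. Freedom from metastasis is not required.
- **Exclusions, 4.2:** uncertain or unclassified grade; recent other malignancy or other concurrent disease affecting the endpoints; loss to follow-up or missing critical data. Metastatic phyllodes tumor at presentation is not named.
- **Enrolment, 5.3 (3):** all eligible consecutive cases enter.

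The DM analysis in 5.4.2 (2) uses Kaplan-Meier and Cox regression on DMFS with death as competing event. Neither it nor the sensitivity analyses in 5.4.2 (6) separate metastasis present at surgery from metastasis that appears later.

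**The concern.** DM is one of three primary outcomes. A patient with lung metastases already documented when she has her mastectomy is eligible, meets the DM definition and adds to the DM rate. Her metastasis is part of her disease at baseline and is not an outcome of follow-up. If she is counted, the rate no longer measures spread after surgery.

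The time-to-event endpoints have a different fault. Her DMFS time is zero or negative and the plan does not say what to do with it. One analyst might count an event at time zero, another might drop her, and a third might follow her to a later lesion. The number of DM events could then differ between the crude rate and DMFS, and two extractors at each of eight centers have no stated rule to apply.

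The exploratory objective in 3.1.3 (2) seeks independent risk factors for DM to inform follow-up and treatment decisions. With prevalent cases among the events, tumor size, surgical procedure or adjuvant chemotherapy can appear to predict later spread when they reflect stage at presentation. The adjustment factors named in 5.3 (5) do not include metastatic status, although that list is open-ended.

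**Working it through.** **1. The text, endpoint by endpoint, for a patient with metastasis at initial surgery**

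| Endpoint | Time condition | Result under the text |
|---|---|---|
| LR, 3.2.1 (1) | after initial surgery | not affected |
| DM and DM rate, 3.2.1 (5)-(6) | none | counted |
| DMFS, 3.2.1 (7) | origin at surgery | time zero or negative, no rule |
| Cumulative rate, 3.2.1 (8) | years after surgery | no rule |

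The accelerated failure time models named as a fallback in 5.4.2 (4) cannot take a time of zero or less. The sensitivity analysis excluding follow-up under 6 months does not remove metastatic patients followed for longer.

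**2. Inputs for the size**

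- The plan states no DM event count, so there is no DM figure to reproduce. Its local recurrence figure does reproduce: 3,500 × 0.11 = 385, against about 380 in 5.4.1.
- Malignant cases: 5.4.1 gives 3,500 patients at about 7:2:1, so 3,500 × 1/10 = 350.
- DM in malignant tumors: 6.5% to 62.5% (section 2.1). 350 × 0.065 = 22.75 and 350 × 0.625 = 218.75, so 23 to 219 events. DM in benign and borderline tumors is left out.
- Share already metastatic at surgery: not in the documents. Assumed 1% to 5% of malignant cases: 350 × 0.01 = 3.5 and 350 × 0.05 = 17.5, so 4 to 18 patients.

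**3. Size on the total-population scale used by 3.2.1 (6)**

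3.5/3,500 = 0.1 and 17.5/3,500 = 0.5 percentage points.

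**4. Size relative to malignant DM events**

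- Low DM rate: 3.5/22.75 = 15%; 17.5/22.75 = 77%.
- High DM rate: 3.5/218.75 = 1.6%; 17.5/218.75 = 8.0%.

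**5. Rates after the fix**, if the background range includes metastases present at surgery. With k such patients, the rate becomes (events − k)/(patients − k).

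| DM rate, malignant | k | Malignant, after | All 3,500, before → after |
|---|---|---|---|
| 6.5% | 3.5 | 19.25/346.5 = 5.6% | 0.65% → 0.55% |
| 6.5% | 17.5 | 5.25/332.5 = 1.6% | 0.65% → 0.15% |
| 62.5% | 3.5 | 215.25/346.5 = 62.1% | 6.25% → 6.16% |
| 62.5% | 17.5 | 201.25/332.5 = 60.5% | 6.25% → 5.78% |

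Section 2.1 gives no timing for its range. If it covers post-surgery events only, the ratios in step 4 are additions to the event count. The top case is then 17.5/(22.75 + 17.5) = 43% of all counted DM events.

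**The case against.** The strongest defence is that DMFS and the cumulative rate start at surgery and that 5.4.2 (2) analyses DM through DMFS, so post-surgery events were evidently meant. That stands in part. A reader might infer that the plan counts prevalent metastases in every DM endpoint and so inflates the early cumulative estimates. The documents support this only for the crude rate. For the timed endpoints the case is undefined, and the effect depends on coding that is not described. The apparent intent does not repair 3.2.1 (5)-(6), which are primary endpoints and say otherwise.

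Other stronger inferences also go beyond the text:

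- **That the database check would miss these patients.** The rule in 6.2.3, "surgery date cannot be later than recurrence date", is given as an example. A metastasis-date rule is not stated, but it is not shown to be absent.
- **That baseline metastases will be systematically found and recorded.** Item (9) of 3.2.2 lists chest CT and PET-CT without saying preoperative, and its examples describe the breast lesion.
- **That the eCRF lacks a baseline field.** Section 6.1.1 leaves the item list open and 6.2.4 defers definitions to a data dictionary. The protocol merely does not list one.
- **That these patients die early and distort OS.** The documents give no survival figure for them, and including them is legitimate in a descriptive cohort.
- **That the DM count is inflated by 77%.** That value pairs the lowest DM rate with the highest assumed share; at the top of the DM range the figure is 1.6%-8%.

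The exclusion in 4.2 (2) for other concurrent diseases could be stretched to cover these patients. It follows a clause on prior other malignancy, however, and spread of the study tumor is not naturally another disease. Finally, risk-factor identification is exploratory, so no confirmatory test is at stake.

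**Conclusion.** The point holds for the definition. The primary DM definition and crude DM rate have no post-surgery limit, and no entry criterion removes patients with metastasis at initial surgery. Prevalent metastases therefore count in the rate, and in DMFS and the cumulative rate they have no stated handling.

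The size is unknown. Under an assumed 1%-5% of about 350 malignant cases, 4-18 patients are affected: about 0.1-0.5 percentage points of the rate in all 3,500, and about 2% to at most 77% relative to malignant DM events. The effect is small if DM is common and material if DM events are few, above all in the malignant stratum and in the DM risk-factor models. The result rests on the 7:2:1 grade mix, the background DM range and the assumed share. Only the first two are in the documents.

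**What to change.** - In 3.2.1 (5)-(8), define DM as distant metastasis first documented after initial surgery.
- Record baseline metastatic status as M0, M1 or not staged, from records where available.
- Remove known M1 patients from the DM rate denominator and from the DM and DMFS risk set, and report them descriptively.
- Keep not-staged patients in the risk set as presumed M0, and add a sensitivity analysis limited to staged M0 patients. About 70% of tumors are expected to be benign and the plan states no staging requirement, so the not-staged group may be large.
- Include a database check that flags any metastasis date on or before the surgery date.

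Showing OS with and without M1 patients is optional.

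The cost is protocol and SAP wording, one extracted field, one check and slightly fewer DM events. Some misclassification will remain among patients who were never staged, and the sensitivity analysis is there to show how much it matters. The change should be made before database lock.
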